# 10.2. Withdrawal From the Study

A subject will be withdrawn from the study for any of the following reasons:

- Lost to follow-up
- Withdrawal of consent
- Subject request to stop study treatment for any reason.
- The investigator or sponsor believes (eg, that for safety or tolerability reasons such as an AE) it is in the best interest of the subject to stop study treatment. The sponsor should be contacted for further discussion and final decision.
- Unacceptable toxicity, as defined in the toxicity management Section 9.5 of this protocol.
- Toxicity that, in the judgment of the investigator, compromises the ability to continue study-specific procedures.
- Pregnancy has been determined in participating female subjects.
- The subject develops clinical hepatitis.
- Discontinuation of the study at the request of the sponsor, DMC, the concerned regulatory agency or Independent Ethics Committee (IEC)/ Institutional Review Board (IRB).

A subject's study treatment may be discontinued if:

- An SAE occurs.
- The subject fails to comply with the protocol or study staff requirements.
- The subject starts disallowed treatment.
- Intercurrent illness that would, in the judgment of the investigator, affect assessments of clinical status to a significant degree.
- The subject requires new onset treatment with one of the medications reported on the list of disallowed medications (see Section 8.1).
- The subject demonstrates VF/viral resistance to any of the ARVs in the HAART regimen; see also Section 9.2.2.1.

If an investigator considers withdrawing a subject from study treatment for 1 of the above reasons, he /she should contact the sponsor for further discussion and final decision, unless the medical condition requires immediate action that cannot wait contact with the sponsor.

Subjects who prematurely discontinue, either during the double-blind active-controlled treatment phase (from Day 1 to Week 48) or during the open-label single-arm D/C/F/TAF treatment phase (from Week 48 up to Week 96), will be required to return to the clinic within 72 hours of stopping study treatment for the ESTD visit.

In addition, a 30-day FU visit will be required for any subject who has an ongoing AE or SAE at the time of his/her last study visit (unless consent is withdrawn).

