5.1. Adverse Events

5.1.1. Definitions

Reported AE parameters and grades are based on the Division of AIDS Table for Grading the Severity of Adult and Pediatric Adverse Events ("**DAIDS AE grading table**"). All AEs will be coded using MedDRA version 19.1.

Events of interest

The EOIs groups include a broad list of terms to identify potential cases. The list of all preferred terms belonging to each AEOI group is provided in Attachment 2. Upon further clinical evaluation additional EOIs might need to be added, and these will be documented in the DPS.

Since many of the terms used to identify potential cases are clinically non-specific, only those retrieved cases that upon medical review are specifically suggestive of /compatible with the AEs of special interest will be commented on in the CSR.

Adverse events of interest (AEOI) groups used for the safety analyses are the following:

- Renal AEOI (for PRT)

Subgroups: laboratory related events,

clinical events

- Bone AEOI (for fractures)

Subgroups: Osteomalacia,

Bone Loss/atrophy,

Fracture, possibly osteoporotic,

Fracture other,

Other Bone Events

- Dyslipidaemia AEOI
- Liver AEOI
- Hyperglycemia AEOI
- Pancreas AEOI
- Severe skin AEOI
- Rash AEOI
- Immune reconstitution inflammatory AEOI
- Coronary artery AEOI
- Ocular AEOI (for posterior uveitis)
- Lipodystrophy AEOI
- Cardiac conduction AEOI

Subgroups: Conduction defects,

Torsade de pointes/QT prolongation

Convulsion AEOI

Adverse Drug Reaction (ADR)

ADRs will be presented. A current list of all ADRs is in Attachment 3. In case multiple lists are available (US and EU definitions), ADRs will be tabulated separately per list.

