Rash AEOI	Acrodynia, Drug Eruption, Generalised erythema, Lupus miliaris disseminatus facei, Mucocutaneous rash, Rash, Rash erythematous, Rash generalised, Rash macular, Rash maculo-papular, Rash maculovesicular, Rash morbilliform, Rash papular, Rash pruritic, Rash rubelliform, Rash scarlatiniform, Red man syndrome, Rash vesicular, Rash follicular, Rash papulosquamous, Dermatitis, Dermatitis acneiform, Dermatitis allergic, Dermatitis herpetiformis, Skin necrosis, Skin reaction
Liver AEOI/Cholestasis and jaundice of hepatic origin	Bilirubin excretion disorder, Cholaemia, Cholestasis, Cholestatic liver injury, Cholestatic pruritus, Drug-induced liver injury, Hepatitis cholestatic, Hyperbilirubinaemia, Icterus index increased, Jaundice, Jaundice cholestatic, Jaundice hepatocellular, Mixed liver injury, Ocular icterus, Parenteral nutrition associated liver disease, Deficiency of bile secretion, Yellow skin

AEOI

AEDECOD (MedDRA v19.1)

Liver AEOI/Hepatic failure, fibrosis and cirrhosis and other liver damage related conditions

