Acute hepatic failure, Acute on chronic liver failure, Acute yellow liver atrophy, Ascites, Asterixis, Bacterascites, Biliary cirrhosis, Biliary cirrhosis primary, Biliary fibrosis, Cholestatic liver injury, Chronic hepatic failure, Coma hepatic, Cryptogenic cirrhosis, Diabetic hepatopathy, Drug-induced liver injury, Duodenal varices, Gallbladder varices, Gastric variceal injection, Gastric variceal ligation, Gastric varices, Gastric varices haemorrhage, Hepatectomy, Hepatic atrophy, Hepatic calcification, Hepatic cirrhosis, Hepatic encephalopathy, Hepatic encephalopathy prophylaxis, Hepatic failure, Hepatic fibrosis, Hepatic hydrothorax, Hepatic infiltration eosinophilic, Hepatic lesion, Hepatic necrosis, Hepatic steato-fibrosis, Hepatic steatosis, Hepatitis fulminant, Hepatobiliary disease, Hepatocellular foamy cell syndrome, Hepatocellular injury, Hepatopulmonary syndrome, Hepatorenal failure, Hepatorenal syndrome, Hepatotoxicity, Intestinal varices, Liver and small intestine transplant, Liver and small intestine transplant, Liver dialysis, Liver disorder, Liver injury, Liver operation, Liver transplant, Lupoid hepatic cirrhosis, Minimal hepatic encephalopathy, Mixed liver injury, Nodular regenerative hyperplasia, Non-alcoholic fatty liver, Nonalcoholic steatohepatitis, Non-cirrhotic portal hypertension, Oedema due to hepatic disease, Oesophageal varices haemorrhage, Peripancreatic varices, Portal fibrosis, Portal hypertensive enteropathy, Portal hypertensive gastropathy, Portal vein cavernous transformation, Portal vein dilatation, Portopulmonary hypertension, Renal and liver transplant, Retrograde portal vein flow, Reye's syndrome, Reynold's syndrome, Splenic varices, Splenic varices haemorrhage, Steatohepatitis, Subacute hepatic failure, Varices oesophageal, Varicose veins of abdominal wall, Anorectal varices, Anorectal varices haemorrhage, Intrahepatic portal hepatic venous fistula, Peritoneovenous shunt, Portal shunt, Portal shunt procedure, Small-for-size liver syndrome, Spider naevus, Splenorenal shunt, Splenorenal shunt procedure, Spontaneous intrahepatic portosystemic venous shunt, Stomal varices, Portal tract inflammation

Liver AEOI / Liver-related investigations, signs and symptoms

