Alanine aminotransferase abnormal, Alanine aminotransferase increased, Ammonia abnormal, Ammonia increased, Ascites, Aspartate aminotransferase abnormal, Aspartate aminotransferase increased, Bacterascites, Bile output abnormal, Bile output decreased, Biliary ascites, Bilirubin conjugated abnormal, Bilirubin conjugated increased, Bilirubin urine present, Biopsy liver abnormal, Blood bilirubin abnormal, Blood bilirubin increased, Blood bilirubin unconjugated increased, Bromosulphthalein test abnormal, Child-Pugh-Turcotte score abnormal, Child-Pugh-Turcotte score increased, Computerised tomogram liver, Foetor hepaticus, Galactose elimination capacity test abnormal, Galactose elimination capacity test decreased, Gamma-glutamyltransferase abnormal, Gammaglutamyltransferase increased, Guanase increased, Hepaplastin abnormal, Hepaplastin decreased, Hepatic artery flow decreased, Hepatic congestion, Hepatic enzyme abnormal, Hepatic enzyme decreased, Hepatic enzyme increased, Hepatic function abnormal, Hepatic hydrothorax, Hepatic hypertrophy, Hepatic mass, Hepatic pain, Hepatic sequestration, Hepatic vascular resistance increased, Hepatobiliary scan abnormal, Hepatomegaly, Hepatosplenomegaly, Hyperammonaemia, Hyperbilirubinaemia, Hypercholia, Hypertransaminasaemia, Kayser-Fleischer ring, Liver function test abnormal, Liver induration, Liver palpable, Liver scan abnormal, Liver tenderness, Mitochondrial aspartate aminotransferase increased, Molar ratio of total branched-chain amino acid to tyrosine, Oedema due to hepatic disease, Perihepatic discomfort, Retrograde portal vein flow, Total bile acids increased, Transaminases abnormal, Transaminases increased, Ultrasound liver abnormal, Urine bilirubin increased, X-ray hepatobiliary abnormal, 5'nucleotidase increased, Blood alkaline phosphatase abnormal, Blood alkaline phosphatase increased, Blood cholinesterase abnormal, Blood cholinesterase decreased, Deficiency of bile secretion, Glutamate dehydrogenase increased, Haemorrhagic ascites, Hepatic fibrosis marker abnormal, Hepatic fibrosis marker increased, Hypoalbuminaemia, Leucine aminopeptidase increased, Liver function test decreased, Liver function test increased, Liver iron concentration abnormal, Liver iron concentration increased, Model for end stage liver disease score abnormal, Model for end stage liver disease score increased, Periportal oedema, Peritoneal fluid protein abnormal, Peritoneal fluid protein decreased, Peritoneal fluid protein increased, Pneumobilia, Portal vein flow decreased, Portal vein pressure increased, Retinol binding protein decreased, Urobilinogen urine decreased, Urobilinogen urine increased

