
AEOI

AEDECOD (MedDRA v19.1)

Liver AEOI / Hepatitis, non infectious

Acute graft versus host disease in liver, Allergic hepatitis, Autoimmune hepatitis, Chronic graft versus host disease in liver, Chronic hepatitis, Graft versus host disease in liver, Hepatitis acute, Hepatitis cholestatic, Hepatitis chronic active, Hepatitis chronic persistent, Hepatitis fulminant, Hepatitis toxic, Ischaemic hepatitis, Lupus hepatitis, Non-alcoholic steatohepatitis, Radiation hepatitis, Steatohepatitis, Granulomatous liver disease, Liver sarcoidosis, Portal tract inflammation

Hyperglycaemia AEOI

Acquired lipoatrophic diabetes, Blood 1,5-anhydroglucitol decreased, Blood glucose increased, Diabetes complicating pregnancy, Diabetes mellitus, Diabetes mellitus inadequate control, Diabetes with hyperosmolarity, Diabetic arteritis, Diabetic coma, Diabetic hepatopathy, Diabetic hyperglycaemic coma, Diabetic hyperosmolar coma, Diabetic ketoacidosis, Diabetic ketoacidotic hyperglycaemic coma, Diabetic metabolic decompensation, Fructosamine increased, Fulminant type 1 diabetes mellitus, Gestational diabetes, Glucose tolerance impaired, Glucose tolerance impaired in pregnancy, Glucose urine present, Glycosuria, Glycosuria during pregnancy, Glycosylated haemoglobin increased, Hyperglycaemia, Hyperglycaemic seizure, Hyperglycaemic unconsciousness, Impaired fasting glucose, Insulin resistance, Insulin resistance syndrome, Insulin resistant diabetes, Insulin-requiring type 2 diabetes mellitus, Ketoacidosis, Ketonuria, Ketosis, Latent autoimmune diabetes in adults, Metabolic syndrome, Monogenic diabetes, Neonatal diabetes mellitus, Pancreatogenous diabetes, Type 1 diabetes mellitus, Type 2 diabetes mellitus, Type 3 diabetes mellitus, Urine ketone body present, Hyperosmolar hyperglycaemic state

AEOI

AEDECOD (MedDRA v19.1)

Dyslipidaemia AEOI

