AE preferred terms (as available in AE Clinical database) are assigned an Adverse Drug Reaction System Organ Class (ADRSOC) and Adverse Drug Reaction (ADRCAT) according to the table below.

Adverse Drug Reaction System Organ Class	Adverse Drug Reaction	Adverse Event Preferred Term
GASTROINTESTINAL DISORDERS	ABDOMINAL DISTENSION	ABDOMINAL DISTENSION
	ABDOMINAL PAIN	ABDOMINAL PAIN
		ABDOMINAL PAIN LOWER
		ABDOMINAL PAIN UPPER
	DIARRHOEA	DIARRHOEA
		FREQUENT BOWEL MOVEMENTS
	DYSPEPSIA	DYSPEPSIA
	FLATULENCE	FLATULENCE
	NAUSEA	NAUSEA
	PANCREATITIS ACUTE	PANCREATITIS
		PANCREATITIS ACUTE
	VOMITING	VOMITING
GENERAL DISORDERS AND ADMINISTRATION SITE CONDITIONS	ASTHENIA	ASTHENIA
	FATIGUE	FATIGUE
HEPATOBILIARY DISORDERS	ACUTE HEPATITIS	HEPATITIS
		HEPATITIS ACUTE
		HEPATOTOXICITY
IMMUNE SYSTEM DISORDERS	(DRUG) HYPERSENSITIVITY	DRUG HYPERSENSITIVITY
		HYPERSENSITIVITY

Approved, Date: 25 April 2018

Adverse Drug Reaction System Organ Class	Adverse Drug Reaction	Adverse Event Preferred Term
	IMMUNE RECONSTITUTION SYNDROME	IMMUNE RECONSTITUTION INFLAMMATORY SYNDROME
		IMMUNE RECONSTITUTION SYNDROME
METABOLISM AND NUTRITION DISORDERS	ANOREXIA	DECREASED APPETITE
	DIABETES MELLITUS	DIABETES MELLITUS
		DIABETES MELLITUS INADEQUATE CONTROL
		TYPE 2 DIABETES MELLITUS
		GLUCOSE TOLERANCE IMPAIRED
	LIPODYSTROPHY	FACIAL WASTING
		FAT REDISTRIBUTION
		FAT TISSUE INCREASED
		LIPOATROPHY
		LIPODYSTROPHY ACQUIRED
		LIPOHYPERTROPHY
		PARTIAL LIPODYSTROPHY
MUSCULOSKELETAL AND CONNECTIVE TISSUE DISORDERS	MYALGIA	MYALGIA
	OSTEONECROSIS	OSTEONECROSIS
NERVOUS SYSTEM DISORDERS	HEADACHE	HEADACHE
PSYCHIATRIC DISORDERS	ABNORMAL DREAMS	ABNORMAL DREAMS
REPRODUCTIVE SYSTEM AND BREAST DISORDERS	GYNAECOMASTIA	GYNAECOMASTIA
		HYPERTROPHY BREAST
SKIN AND SUBCUTANEOUS TISSUE DISORDERS	ANGIOEDEMA	ALLERGIC OEDEMA
		ANGIOEDEMA

46

Adverse Drug Reaction System Organ Class	Adverse Drug Reaction	Adverse Event Preferred Term
		CIRCUMORAL OEDEMA
		CONJUNCTIVAL OEDEMA
		CORNEAL OEDEMA
		EPIGLOTTIC OEDEMA
		EYE OEDEMA
		EYE SWELLING
		EYELID OEDEMA
		FACE OEDEMA
		GINGIVAL OEDEMA
		GINGIVAL SWELLING
		GLEICH'S SYNDROME
		HEREDITARY ANGIOEDEMA
		LARYNGEAL OEDEMA
		LARYNGOTRACHEAL OEDEMA
		LIP OEDEMA
		LIP SWELLING
		OCULORESPIRATORY SYNDROME
		OEDEMA MOUTH
		OROPHARYNGEAL SWELLING
		PALATAL OEDEMA
		PERIORBITAL OEDEMA
		PHARYNGEAL OEDEMA
		SCLERAL OEDEMA
		SMALL BOWEL ANGIOEDEMA
		SWELLING FACE
		SWOLLEN TONGUE

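### The Liver event-of-interest lists in the SAP omit the plain preferred term Hepatitis, which the SAP's own adverse drug reaction table counts as acute hepatitis

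*SAP*

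**What the plan says.** SAP section 5.1.1 sets out how events of interest are found. On scope it says: "The EOIs groups include a broad list of terms to identify potential cases". On where the terms are held: "The list of all preferred terms belonging to each AEOI group is provided in Attachment 2". The same section accepts that many of the terms are clinically non-specific. It leaves specificity to medical review, and only retrieved cases that the review finds compatible are discussed in the study report. Further events of interest may be added after clinical evaluation and recorded in the data presentation specifications (DPS).

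Attachment 2 gives the Liver AEOI as four lists:

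- cholestasis and jaundice, where the only hepatitis entry is in the run "Drug-induced liver injury, Hepatitis cholestatic, Hyperbilirubinaemia, Icterus index increased";
- hepatic failure, fibrosis, cirrhosis and other damage, with "Hepatic steatosis, Hepatitis fulminant, Hepatobiliary disease" among its entries, two steatohepatitis terms, and Hepatotoxicity;
- liver-related investigations, signs and symptoms, with no hepatitis term where the alphabet would place one: "Hepatomegaly, Hepatosplenomegaly, Hyperammonaemia, Hyperbilirubinaemia";
- non-infectious hepatitis, which includes "Chronic hepatitis, Graft versus host disease in liver, Hepatitis acute, Hepatitis cholestatic, Hepatitis chronic active, Hepatitis chronic persistent".

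Attachment 3 maps adverse event preferred terms to ADRs. Under hepatobiliary disorders, the reaction "ACUTE HEPATITIS" is made up of Hepatitis, Hepatitis acute and Hepatotoxicity. SAP section 5.1.2 plans incidence tabulations for the AEOI and, separately, for the ADRs.

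**The concern.** The two attachments classify the same event differently. An event coded to plain Hepatitis is a liver reaction under Attachment 3 and is not a liver event of interest under Attachment 2. A report built literally from these lists could show an acute hepatitis in one table with no matching subject in the liver table. Because section 5.1.1 ties the report's commentary to retrieved cases, that subject would also miss the medical review meant to judge whether the event is a true liver case.

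The liver is a stated interest of the study. Protocol section 1.7 notes that liver toxicity related to cobicistat was seen preclinically, and Protocol section 10.2 lists among the withdrawal reasons: "The subject develops clinical hepatitis". A liver summary that leaves out the plainest hepatitis term does not fully serve that interest.

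**Working it through.** No sample size, power or alpha figure is involved. The check is a comparison of term lists, then a bound on its effect.

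**Step 1: the Liver AEOI lists.** Splitting the four lists in SAP Attachment 2 into single entries gives:

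| Liver AEOI list | Entries | Entries containing the word hepatitis |
|---|---|---|
| Cholestasis and jaundice | 17 | 1 (Hepatitis cholestatic) |
| Failure, fibrosis, cirrhosis, other damage | 90 | 3 (Hepatitis fulminant; two steatohepatitis terms) |
| Investigations, signs, symptoms | 94 | 0 |
| Hepatitis, non infectious | 20 | 14, all qualified |

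Total: 17 + 90 + 94 + 20 = 221 entries, or 206 distinct terms once repeats are removed.

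**Step 2: match against Attachment 3.** Exact match, ignoring case, of the three terms that make up the acute hepatitis ADR:

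| ADR term | In the Liver AEOI? |
|---|---|
| Hepatitis acute | Yes, non-infectious hepatitis list |
| Hepatotoxicity | Yes, failure/fibrosis/cirrhosis list |
| Hepatitis | No, in none of the four lists |

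Coverage is 2 of 3. With the one term added, the non-infectious hepatitis list goes from 20 to 21 entries and coverage becomes 3 of 3.

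**Step 3: could the omission be intended?** Two explanations can be tested against the text.

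- *Too vague a term.* Section 5.1.1 asks for breadth and tolerates non-specific terms. The Liver lists keep Liver disorder, Ascites, Spider naevus and Hypoalbuminaemia, none of which is more specific than Hepatitis.
- *Possibly infectious.* Hepatitis acute and Chronic hepatitis say nothing about cause either, and both are listed. Attachment 3 itself treats Hepatitis as a hepatobiliary drug reaction.

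Neither explains leaving out this one term.

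**Step 4: could it be lost text?** The attachments were read from PDF, and parts of Attachment 2 (severe skin, ocular) are visibly out of order. The non-infectious hepatitis list shows no gap: its main run is alphabetical, and Hepatitis would fall directly before Hepatitis acute, where the text is continuous. An artefact is unlikely but cannot be fully excluded without the source table.

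**Step 5: size.** One subject is 1/335 = 0.3% of a planned arm. The documents give no hepatitis rate. Assuming that 0 to 1% of an arm has a hepatitis-type event gives 0 to 0.01 × 335 = 3.35, so 0 to about 3 subjects per arm. This is a ceiling: only subjects whose event is coded to the bare term, and who have no other listed liver term, drop out of the summary. The true number may be zero.

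**The case against.** The strongest reply is that very little is lost. SAP section 5.1.2 plans incidences by system organ class and preferred term for all adverse events, serious events, events by grade, related events and events leading to a stop of medication, plus an ADR table and a full listing. Liver injury is also examined independently of event coding through the hepatic laboratory parameters (5.2.1), and through the worst-grade cross-tabulations and the Hy's law analysis (5.2.2). A subject withdrawn for clinical hepatitis should also be visible in disposition and among the permanent stops. No formal testing is done on adverse events. All of this stands and limits the point to one descriptive grouping and the review attached to it.

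A second reply is that the DPS can add terms. That route exists, so Attachment 2 is not closed. But it is optional, no stated rule would trigger this addition, and the DPS is not among the documents.

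Three stronger readings are tempting and are not supported:

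- *That a reported hepatitis disappears from the safety report.* It does not; the tables above would carry it, and a subject with any other listed liver term remains in the Liver AEOI summary.
- *That the omission could remove most of the clinical liver cases.* The lists also hold clinical terms such as jaundice, hepatic steatosis, hepatomegaly and drug-induced liver injury. The documents give no rate for these, so no share can be calculated.
- *That every ADR term must also be an AEOI term.* Neither document says so, and other ADR terms also lie outside the corresponding AEOI list: Fat tissue increased (lipodystrophy) and Immune reconstitution syndrome (immune reconstitution). The mismatch alone is therefore not the error. The error is that the omitted term fits the SAP's own description of what the Liver list is for.

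**Conclusion.** The point holds as a list inconsistency with a narrow consequence. The Liver AEOI omits plain Hepatitis while covering the other two terms that Attachment 3 treats as the same reaction, and nothing in section 5.1.1 justifies the difference. As written, a subject whose only liver event carries that code is in the ADR table but not in the Liver AEOI summary, and is not among the retrieved cases sent for medical review.

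The effect is probably very small. The ceiling of about 3 subjects per arm rests on an assumed rate rather than on a figure in the documents. No hypothesis, confidence interval or efficacy conclusion depends on it. The conclusion also assumes that the lists were extracted completely and that the DPS has not already added the term.

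**What to change.** Add Hepatitis to the Liver AEOI list headed Hepatitis, non infectious, in SAP Attachment 2. If its exclusion is intended, state the reason there instead.

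Apply the amended list to all periods named in SAP section 5: Baseline to Week 48, Week 48 to Week 96 and Baseline to Week 96 for the initial arm, and Baseline to Switch and Switch to Week 96 for the late-switch arm. Footnote any difference from the counts in the Week 48 report.

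The cost is one line of metadata. The term may occasionally retrieve a hepatitis later judged infectious, which the planned medical review handles. A short reconciliation with the Week 48 counts may be needed; the Week 48 SAP is not among the documents, so whether its list had the same gap cannot be checked here.
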